5.6.3.2. Vital Signs and Physical Examination Findings

Vital signs will be measured at visits as per the schedule of events in the protocol. Descriptive statistics of the observed value and change from baseline of the vital signs will be summarized by treatment group.

5.6.3.3. Electrocardiogram

No analysis is planned.

5.6.3.4. Other Safety Parameters

No analysis is planned.

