## SAFETY EVALUATIONS

Safety assessments will consist of adverse events (including serious adverse events), physical examinations, vital signs, height and weight, electrocardiograms, clinical safety laboratory assessments, suicidal ideation or behavior using the Columbia-Suicide Severity Rating Scale, and concomitant medication review. Injection site reactions, hypersensitivity reactions, infections, tuberculosis evaluations, and pregnancy testing will be performed or collected as specified in the Schedule of Activities.

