Hepatitis B and C serology l	X															
HIV Ab test	X															
Hematology	X	X	X		X	X		X		X				X	X	X
Chemistry	X	X	X		X	X		X		X				X	X	X
Lipid panel n		X						X						X	X	X
Hs-CRP		X	X			X		X		X				X	X	X
HbA1c		X						X						X	X	X

Phase	Screening a	Placebo b				Active Treatment b								Follow-Up b,c		
Week		0	4	8	12	16	20	24	28	32	36	40	44 (last dose)	48 (Final Efficacy)	Early Term.	56 (Final Safety)
Clinical Pharmacology and Biomarker Assessments p																
Serum guselkumab concentration		X	X			X				X				X	X	X
Anti-guselkumab antibodies		X	X			X				X				X	X	X
Serum biomarkers		X	X			X				X				X		
Optional Substudies e																
Skin biopsy p		X				X								X		
Tape stripping		X	X			X				X				X		
Whole blood (pharmacogenomics) q		X														
Ongoing Participant Review																
Concomitant therapy	X	X	X	X	X	X	X	X	X	X	X	X	X	X	X	X
Adverse events	X	X	X	X	X	X	X	X	X	X	X	X	X	X	X	X

a: The screening visit should occur within approximately 4 weeks before the Week 0 visit.

b: All post-baseline visits will have a visit window of  $\pm 7$  days counting from Week 0 as Day 1.

c: If a participant permanently discontinues study drug intervention prior to the Week 16 visit, they should be encouraged to return for all remaining study visits through Week 16, and the participant should also return for a final visit to perform assessments under the Week 56/final safety visit approximately 12 weeks after the last study intervention administration. If a participant permanently discontinues study drug at or after the Week 16 visit, they should complete the Week 48/final efficacy visit assessments at the time of discontinuation, or as soon as possible, and also return for a final safety visit to perform assessments under the Week 56/final safety visit approximately 12 weeks after the last study intervention administration.

d: All study procedures and evaluations should be completed before administration of study drug.

e: ICFs must be signed before the first study-related activity. The optional skin biopsy, tape stripping, and pharmacogenomics substudies will use separate ICFs.

f: Details may be found in the Photography Manual.

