5.6. Other Safety Analyses

Safety will be assessed by summarizing the occurrences and type of AEs, vital signs (pulse, blood pressure, and weight), examining the changes in the laboratory parameters.

In all the safety analysis, participants who were randomized and received at least 1 (partial or complete) dose of study agent administration will be included and analyzed according to the treatment they actually received, regardless of the treatments they are randomized to.

For all continuous safety variables, descriptive statistics by intervention group will include the N, mean, standard deviation, median, minimum, and maximum. Categorical variables will be summarized by intervention group using frequency counts and percentages.

There are 2 DBLs in this study, respectively, at Week 16, and final DBL at Week 56. Depending on the safety data categories, the cumulative safety data will be analyzed through different study periods which may include, but are not limited to safety data through Week 16, through Week 56. Tabular summaries of safety events for key study periods are in general presented as follows:

Summaries Through Week 16

Safety data through Week 16 will be analyzed according to the following treatment groups:

1. **Placebo:** Participants who received placebo only and no guselkumab through Week 16.
2. **Guselkumab CCI** at Weeks 0, 4, and then **CCI** Participants who received guselkumab **CCI** **CCI** through Week 16.

For participants who started treatment with placebo only but later received guselkumab prior to Week 16 inadvertently, the safety events/measurements on and after the first dose of guselkumab, will be excluded from the data summaries through Week 16. Only the safety events/measurements that occurred while the participants had been receiving placebo only will be included in the data summaries through Week 16.

Summaries Through Week 56

Safety data through Week 56 will be analyzed according to the following treatment groups:

1. **Placebo → Guselkumab CCI CCI** Participants who started treatment with placebo and later received treatment with guselkumab (due to crossed over or inadvertently) at Weeks 16 and 20 then **CCI** through Week 56. All the safety events/measurements that occurred on and after the first dose of guselkumab up to Week 56 will be included in this group.
2. **Guselkumab CCI** Participants who received guselkumab **CCI** at Week 0, 4 and then **CCI** **CCI** through Week 56 for those randomized to guselkumab.

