5.6.2. Adverse Events

Adverse Events (AEs) that occurred any time over the study will be reported and coded using Medical Dictionary for Regulatory Activities (MedDRA). Analyses of AEs will be performed on those events that are considered treatment emergent. Treatment emergent AEs are those AEs that occurred after the start of initial study agent administration and those AEs that were present at baseline but worsened in severity after the start of initial study agent administration. Treatment emergent AEs will be summarized by MedDRA system organ class, preferred term, and actual treatment group. The numbers of participants reporting at least 1 event of the following treatment emergent AE categories will be summarized:

- Any AEs
- Serious adverse events (SAEs)
- AEs that are reasonably related to study agent
- AEs of severe intensity
- AEs that led to permanent discontinuation of study agent administration
- Injection-site reactions
- AEs of psoriasis

These summary tables will provide the count and percentage of participants with 1 or more of the specified AEs by treatment group. To adjust for the different duration of follow-up among treatment groups, the AE rates per hundred participant-years of follow-up will also be provided for the above AE categories, Malignancy, Tuberculosis, MACE, infections, serious infections and IBD.

All AE summary tables will include average weeks of follow-up and average number of study agent administrations for each treatment group.

In addition to the summary tables, listings of participants with the following AEs will also be provided:

- SAEs
- AEs leading to permanent discontinuation of study agent
- Opportunistic infection
- Malignancies (non-melanoma skin cancer and other malignancies)
- Death
- Suicidal ideation and behavior
- Possible serum sickness-like reactions and anaphylactic reactions.

Any unfavorable or unintended sign that occurs at the injection site is an injection site reaction and will be recorded as an AE.

Adverse events of psoriasis include any event of erythrodermic psoriasis, pustular psoriasis, guttate psoriasis, inverse psoriasis, palmo-plantar psoriasis and worsening or exacerbation of psoriasis.

In addition, impact of weight on safety will be evaluated for selected treatment emergent AE categories based on baseline weight (≤ 90 kg, >90 kg).

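### The C-SSRS is collected at every visit as a safety assessment, but no output from the scale is planned; suicidality is reported only through adverse events

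*SAP*

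**What the plan says.** **Collection.** The Safety Evaluations paragraph of the protocol synopsis lists "clinical safety laboratory assessments, suicidal ideation or behavior using the Columbia-Suicide Severity Rating Scale, and concomitant medication review" among the safety assessments. The Schedule of Activities (protocol 1.3) marks the C-SSRS row in every column. Protocol 8.2.6 describes the scale as a screening tool, and in the same sentence gives it a role in the overall evaluation of safety during the study.

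**Analysis.** Protocol 9.4.5 covers AEs, laboratory tests, vital signs and physical examinations. In SAP 5.6, safety is "assessed by summarizing the occurrences and type of AEs, vital signs (pulse, blood pressure, and weight), examining the changes in the laboratory parameters". SAP 5.6.3.4 (Other Safety Parameters) says "No analysis is planned". The SAP does not mention the C-SSRS anywhere, including its abbreviation list.

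**Suicidality through AEs.** SAP 5.6.2 states: "Treatment emergent AEs will be summarized by MedDRA system organ class, preferred term, and actual treatment group". It adds that "listings of participants with the following AEs will also be provided", and one item under that lead-in is "Suicidal ideation and behavior".

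**The concern.** A scale given to every participant at every visit is meant to pick up suicidal ideation and behaviour systematically, without relying on spontaneous reports. Under this plan its results reach the study report only after a second step, the investigator's decision to record a finding as an AE.

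Three things are lost:

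- Weeks 0 to 16 are the only period with a comparator, and no result from the scale by arm is planned for them.
- Protocol 8.2.6 lets participants with a positive pre-dose rating be randomized if they are judged not to be at risk. AE outputs do not show movement from that starting category.
- Protocol 7.1 uses ideation levels 4 and 5, or any suicidal behaviour, as a trigger for considering discontinuation of study drug. No output counts who reached that trigger on the scale.

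SAP 5.8.1 plans no data monitoring committee. The unblinded committee in protocol 8.3.3 is described for anticipated events, which here means worsening of psoriasis. The study report is therefore the natural place for a by-arm C-SSRS result.

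**Working it through.** The question is whether a planned output exists, so the check is a comparison of texts. The plan gives no figure of its own to reproduce.

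**Step 1. Is the scale collected after baseline?** The C-SSRS row in the Schedule of Activities has screening (1), Weeks 0 to 48 every four weeks (13), Early Termination (1) and Week 56 (1). That is 1 + 13 + 1 + 1 = 16, and all 16 columns are marked.

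**Step 2. Is any output from it planned?**

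| Place | Planned content | C-SSRS output |
|---|---|---|
| Protocol 9.4.5 | AEs, laboratory, vital signs, physical examination | None |
| SAP 5.6 | AEs, vital signs, laboratory changes | None |
| SAP 5.6.2 | AE tables, AE rates, AE listings | None from the scale; one AE-based suicidality listing |
| SAP 5.6.3.1 | Laboratory tests | None |
| SAP 5.6.3.2 | Vital signs | None |
| SAP 5.6.3.3 | ECG: no analysis | None |
| SAP 5.6.3.4 | Other safety parameters: no analysis | None |

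The total is zero. That SAP 5.6.3.4 covers the C-SSRS is an inference, because it is the residual safety heading. The conclusion rests mainly on the scale's absence from the rest of the SAP.

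Two neighbouring assessments help to calibrate this. The ECG also has no planned analysis, but it is done only at screening, so there is no change to report. Vital signs are taken at every visit, as the C-SSRS is, and they do get descriptive summaries.

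**Step 3. Which ratings reach the AE outputs?** Protocol 8.2.6 asks for an AE when the investigator considers a finding new, or a worsening, and clinically significant. The wording leaves open whether clinical significance is also required of a new finding. The general AE definition in protocol 8.3.1 and Appendix 5 favours the broad reading, in which a new finding is enough.

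| Post-baseline rating | Narrow reading | Broad reading |
|---|---|---|
| New, clinically significant | AE | AE |
| New, judged not significant | No output | AE |
| Worse than pre-dose, significant | AE | AE |
| Worse than pre-dose, judged not significant | No output under 8.2.6 | No output under 8.2.6, though the general definition could capture it |
| Positive, unchanged from pre-dose | No output | No output |

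The rows without output most plausibly hold ideation levels 1 to 3, for which 8.2.6 asks only for the investigator's risk assessment. Levels 4 and 5 and suicidal behaviour also require referral to a mental health professional and discussion with the medical monitor.

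**Step 4. Size.** The number affected equals the number of participants with a positive post-baseline rating multiplied by the share of them with a rating not recorded as an AE. The documents give neither factor. The range runs from none (no positive ratings, or all recorded as AEs) to every participant with a positive rating.

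**The case against.** **The general format sentence.** SAP 5.6 says that categorical safety variables are summarized by group with counts and percentages, and a C-SSRS category is such a variable. That sentence sets a format for whatever is summarized. It does not create a C-SSRS table, and the residual section says there is no analysis.

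**The scale is a monitoring tool.** Its specified uses are eligibility, risk assessment, referral and considering discontinuation. The safety endpoint is AEs and SAEs. Suicidality is not among the study-drug risks in protocol 2.3.1 or the events of special interest in 8.3.5. All of this stands and keeps the point small. But 8.2.6 also gives the scale a part in the safety evaluation, and that part has no output.

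**Suicidality is already reported.** AEs are tabulated by system organ class, preferred term and arm, and suicidality has its own listing. This also stands. The listing is restricted to AEs, however, so an unrecorded rating is not in it. On the broad reading of 8.2.6 the remaining gap is narrow.

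**Week 16 attribution.** A reader might infer that a placebo participant's Week 16 rating would be counted as crossover data, because SAP 5.6 says of the crossover group: "All the safety events/measurements that occurred on and after the first dose of guselkumab up to Week 56 will be included in this group". The documents do not support a separate concern here. The Schedule of Activities footnote says "All study procedures and evaluations should be completed before administration of study drug", so a Week 16 rating precedes the first guselkumab dose and belongs to placebo. Any same-day date handling applies to all Week 16 safety measurements alike.

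**Conclusion.** The point holds as a gap in reporting and is minor. The C-SSRS is collected throughout, no output from it is planned, and a positive rating not recorded as an AE would not appear in the report. This is more than missing detail, because a programmer who follows the SAP as written would leave these data out.

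A reader might infer that suicidality goes unreported or unmonitored, or that a safety signal is hidden in one arm. The documents do not support that. Suicidality AEs are tabulated and listed, participant-level monitoring in 8.2.6 and 7.1 is intact, and no direction of bias is shown. Nor does the volume of scheduled ratings measure the loss, since a scheduled rating is not a missed event.

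The conclusion assumes that SAP 5.6.3.4 is where the scale would fall, and that the suicidality listing is filled from AE records, as its lead-in says. The number of participants affected remains unknown.

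**What to change.** In SAP 5.6.3.4, replace the no-analysis statement, for the C-SSRS, with two descriptive outputs by actual treatment group:

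1. A table of worst post-baseline category against worst pre-dose category (screening and Week 0). Categories: none, ideation levels 1 to 5, suicidal behaviour, and non-suicidal self-injury. Present it through Week 16 and through Week 56, in the groups that SAP 5.6 already defines.
2. A listing of participants with any positive post-baseline rating, with a flag for whether it was also recorded as an AE. The flag shows how sites applied 8.2.6, so no protocol change is needed.

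No hypothesis test is needed, and the Type I error plan is unaffected. The cost is one SAP paragraph and a small amount of programming on data already captured on the electronic device.

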5.7. Other Analyses

5.7.1. Pharmacokinetics

Blood samples for measuring serum guselkumab concentrations will be collected from all participants at scheduled visits as indicated in the Schedule of Events in the protocol.

The PK analysis will be based on participants who received at least 1 administration of guselkumab and had at least one evaluable serum sample. No imputation of missing concentration data will be performed, that is, data summaries will be based on the observed data.

For analysis on serum guselkumab concentrations, descriptive statistics, including arithmetic mean, SD, median, interquartile range, minimum, and maximum will be provided, where appropriate, by treatment group at each serum sampling time. The PK concentration data may also be displayed graphically. The following analyses will be performed by treatment group as appropriate:

- Summary of serum guselkumab concentrations at each visit by treatment group

- Participants with serum guselkumab concentration below the lowest quantifiable concentration in a sample will be summarized by treatment group overtime.
- Summary of serum guselkumab concentrations overall and by baseline weight (≤ 90 kg, >90 kg) will be summarized by treatment group overtime.
- Plot of median serum guselkumab concentrations over time by treatment group

In addition, the relationship between serum guselkumab concentrations and safety or efficacy may be explored.

For summary statistics of serum guselkumab concentrations, concentration values below the lower limit of quantification will be treated as zero. Once a Participant meets one of the following dosing deviation criteria, the participant's data will be excluded from the by-visit data analyses from that point onwards.

Dosing deviation criteria:

- Discontinue ███ guselkumab administrations.
- Skipped an ███ guselkumab administration.
- Received an incomplete/ incorrect ███ dose.
- Received an incorrect ███ study agent.
- Received an additional ███ guselkumab dose.

In addition, if a participant has an administration outside of visit windows (Section 5.1.1), the concentration data collected at and after that visit will be excluded from the by-visit data analyses. Additional exclusions for incongruous PK data to be implemented based on Janssen SOP-07948.

Population PK analyses will be performed to characterize the disposition characteristics of guselkumab based on the guselkumab concentration data from PSO studies. Data may be combined with other selected studies to support a relevant structural model. A detailed analysis plan for population PK analysis will be developed separately, and a stand-alone technical report will be written to summarize the results of the population PK analysis.

PK analyses presentation

PK analyses will be summarized through the following time periods:

- Through Week 16
- Through Week 48

For the analyses, a Participant is included in one and only one treatment group on the basis of the treatment regimen followed. The description of treatment groups are as follows:

1. **Placebo → Guselkumab** ███ ███ Participants randomized to placebo and were switched over to Guselkumab ███ ███ (due to CO) at Week 16.

2. **Guselkumab** [REDACTED] at Week 0, Week 4, and then [REDACTED] Participants randomized to guselkumab [REDACTED] at Week 0, Week 4, and then [REDACTED] and received guselkumab [REDACTED] [REDACTED] throughout.

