g: Participants with no prior diagnosis of rheumatologist confirmed PSA will complete the PEST at screening. If screening PEST score  $\geq 3$ , participants will complete PsAID-12 at Week 0 (baseline) and for the remainder of study visits as specified. If screening PEST score  $< 3$ , participants will complete PEST at Week 0 (baseline) and for the remainder of study visits as specified. Participants with prior diagnosis of rheumatology confirmed PSA will complete the PsAID-12 starting at Week 0 (baseline) and for the remainder of study visits as specified.

h: Chest X-ray should be performed at screening if the participant does not have a chest X-ray within 12 weeks prior to the first administration of study intervention.

i: All participant questionnaires should be completed before any other tests, procedures, or evaluations on the day of the visit for baseline and post-baseline visits. The 'Baseline/Screening' version of the C-SSRS will be performed at the screening visit prior to all questionnaires. At Week 0 and all subsequent visits, the 'Since Last Visit' version of the C-SSRS will be performed after all other questionnaires.

j: Participants of childbearing potential must have a negative pregnancy test before randomization and before study drug administration at study visits.

k: Interferon gamma release assay testing includes either QuantiFERON-TB® or T-SPOT.TB®. Interferon gamma release assay testing is not required at screening for participants with a history of treated latent TB or ongoing treatment for latent TB.

- l: For details related to hepatitis B screening and eligibility, refer to Appendix 3. For details related to hepatitis C screening and eligibility, refer to Exclusion Criterion 32.
- m: Laboratory tests are listed in Appendix 2 of the protocol.
- n: Participants must fast (i.e., no food or beverages [except water]) for at least 8 hours before blood is drawn for lipid panel unless there is medical contradiction. All other visits can be non-fasting.
- o: All blood samples must be collected before study agent administration at visits when a study agent administration is scheduled. Blood collected from 1 venipuncture will be divided into multiple aliquots of serum for the measurement of guselkumab concentration, antibodies to guselkumab, and a back-up sample. Biomarker blood collection will be divided into 3 aliquots. Details will be provided in the Laboratory Manual.

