#### 6.4. Study Intervention Compliance

In this study, the **CC** investigational product (IP, guselkumab/placebo) will be administered at the study site.

Compliance will be assessed by direct questioning during the site visits and documented in the source documents and eCRF. Deviation(s) from the prescribed dosage regimen should be recorded in the eCRF.

During the study, the investigator or designated study research personnel will be responsible for providing additional instruction to reeducate any participant who is not compliant with taking the study intervention.

Compliance with the treatment schedule is strongly encouraged. It is understood that treatment may be interrupted for health-related or safety reasons.

- If, for any reason, a participant cannot receive the study intervention at the scheduled visit, the participant must make every effort to still come in for the scheduled assessments for that visit.
- In general, the dose should be administered within approximately 2 weeks of that scheduled visit.
- The participant should then resume the normal study schedule relative to the baseline visit (Week 0).

In the case when a participant does not come into the study site for a scheduled visit, the site will follow up with that participant. Due diligence could include telephone calls, certified letters, and email requests. Measures taken to obtain follow-up information must be documented.

- Study site personnel will keep a log of all study intervention dispensed and will compare the amount of study intervention dispensed with the amount returned.

All post-baseline visits will have a visit window of approximately  $\pm 7$  days counting from Week 0 as Day 1. If a study visit occurs outside this window, the Sponsor should be consulted about how the participant should resume his or her normal dose schedule.

Information regarding study intervention administrations that are administered outside of the scheduled windows or missed will be recorded. Participant charts and worksheets may be reviewed and compared with the data entries on the eCRFs to ensure accuracy.

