1.2. Study Design

This is a Phase 3b, multicenter, randomized, double-blind, placebo-controlled study designed to evaluate the efficacy and safety of guselkumab versus placebo in participants with low BSA moderate plaque psoriasis with special site involvement.

Approximately 300 eligible participants will be randomized in a 2:1 ratio to receive either guselkumab [REDACTED] at Weeks 0 and 4 and then [REDACTED] or placebo (Figure 1). Randomization will be stratified by qualifying special sites (i.e., scalp, face, intertriginous, and genital) with approximately 25% of participants per each special site. If participants present with qualifying moderate psoriasis in multiple special sites, they will be allocated to the special site that is most severe, as determined by the participant. The study will aim to enroll no less than approximately 20% of participants from diverse racial-ethnic backgrounds (i.e., self-identify as non-white/non-Caucasian descent) to reflect the North American Census population.

There will be 2 treatment groups:

- A guselkumab group who will receive guselkumab [REDACTED] [REDACTED] at Weeks 0 and 4 and then [REDACTED] through Week 44. Placebo will be administered at Week 16 to maintain the blind.
- A placebo group who will receive placebo at Weeks 0, 4, and 12 after which they will cross over to receive guselkumab at Weeks 16, 20, 28, 36, and 44.

Further details on active and blinding study intervention administrations for both treatment groups are provided in Section 6.

There will be 2 database locks (DBLs) in this study, at Weeks 16 and 56. After all participants have completed the Week 16 visit (or discontinued from the study), a Week 16 DBL will be performed, and unblinded data will only be made available to select Sponsor and Contract Research Organization (CRO) team members involved with analysis of the data and preparation of analyses for the Week 16 DBL. All other Sponsor, site, and CRO personnel directly involved

with study conduct will remain blinded to treatment assignments until the Week 56 DBL and related analyses have been completed. A diagram of the study design is provided in [Figure 1](#).

[figure not shown]
Week 0 through Week 16 (Placebo Controlled Period)

- Group I (n=200): guselkumab CCI CC at Weeks 0, 4, and 12. Placebo will be administered at Week 16 to maintain the blind.
- Group II (n=100): placebo at Weeks 0, 4, and 12 followed by guselkumab CCI at Weeks 16

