From Week 0 through Week 44 (Placebo Controlled and Active Treatment Period)

- Group I (n=200): guselkumab group who will receive guselkumab CCI CC at Weeks 0 and 4 and then CCI through Week 44. Placebo will be administered at Week 16 to maintain the blind.
- Group II (n=100): placebo group who will receive placebo at Weeks 0, 4, and 12 after which they will cross over to receive guselkumab at Weeks 16, 20, 28, 36, and 44.

Figure 1: Schematic Overview of the Study

A placebo control will be used to establish the frequency and magnitude of changes in clinical endpoints that may occur in the absence of active intervention. Randomization will be used to minimize bias in the assignment of participants to intervention groups, to increase the likelihood that known and unknown participant attributes (eg, demographic and baseline characteristics) are

evenly balanced across intervention groups, and to enhance the validity of statistical comparisons across intervention groups. Blinded intervention will be used to reduce potential bias during data collection and evaluation of clinical endpoints. Comparisons are planned between guselkumab and placebo at Week 16.

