5.1.1. Visit Windows

5.1.1.1. Visit Windows for Dosing and PK Analysis

All post-baseline visits from Baseline through Week 16 will have a visit window of ± 7 days counting from week 0 as Day 1. If a study visit occurs outside this window, the Sponsor should be consulted about how the participant should resume his or her normal dose schedule.

For PK analyses, if a participant has an administration outside the visit window at a visit, the concentration data collected at and after that visit will be excluded from the by-visit data analyses.

Information regarding study intervention administrations that are administered outside of the scheduled windows or missed will be recorded. Participant charts and worksheets may be reviewed and compared with the data entries on the eCRFs to ensure accuracy.

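### The SAP's PK exclusion rule is not limited to guselkumab injections, so read literally a late placebo injection removes on-schedule guselkumab concentrations from the by-visit summaries

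*SAP*

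**What the plan says.** SAP 5.7.1 lists dosing deviations after which a participant's data leave the by-visit analyses for good. It then adds a timing rule: "if a participant has an administration outside of visit windows (Section 5.1.1), the concentration data collected at and after that visit will be excluded". SAP 5.1.1.1 carries the same rule: "if a participant has an administration outside the visit window at a visit, the concentration data collected at and after that visit will be excluded". Neither sentence names the agent.

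The window that both rely on is in SAP 5.1.1.1: "All post-baseline visits from Baseline through Week 16 will have a visit window of" ±7 days. Footnote b of the protocol's Schedule of Activities has no such end point: "All post-baseline visits will have a visit window of" ±7 days.

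On conduct, Protocol 6.4 asks a participant who cannot be dosed to attend the visit anyway, and continues: "In general, the dose should be administered within approximately 2 weeks of that scheduled visit". Footnote o of the Schedule of Activities fixes the order of sampling and dosing: "All blood samples must be collected before study agent administration at visits when a study agent administration is scheduled".

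On the schedule, SAP 1.2 gives "Group II (n=100): placebo at Weeks 0, 4, and 12 followed by guselkumab" and says that these participants "cross over to receive guselkumab at Weeks 16, 20, 28, 36, and 44". The guselkumab group receives one blinding placebo injection, at Week 16. Serum concentration is sampled at Weeks 0, 4, 16, 32, 48 and 56 and at early termination. SAP 5.7.1 summarises PK through Week 16 and through Week 48.

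**The concern.** A placebo injection contains no guselkumab, so its timing cannot alter a later guselkumab concentration. A programmer who applies the rule as written would still drop every later concentration for that participant. The contrast within SAP 5.7.1 invites this literal reading: three of the five dosing-deviation criteria just above name guselkumab, and the timing sentence does not.

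Three related gaps sit in the same text:

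- The rule reaches back to the sample taken at the visit itself, although that sample is drawn before the dose whose lateness triggers the exclusion.
- On the SAP's own wording, the window stops at Week 16. It therefore covers every post-baseline placebo injection but not the guselkumab doses after Week 16, which determine the Week 32 and 48 values.
- The rule is keyed to injections. No injection is scheduled at Week 32 or 48, so a mistimed sample there cannot trigger it.

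At stake is the number of usable values in the by-visit concentration summaries, including those by baseline weight group.

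**Working it through.** The plan states no figure on this point, so there is none to reproduce. I applied the rule literally to the schedule and then sized the loss.

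**Inputs.** The placebo-group injections are as quoted. The guselkumab group's later dosing interval is blacked out. I take its injection visits to match those of the placebo group, because its only listed blinding injection is at Week 16 and the last dose is at Week 44. The baseline injection at Week 0 is not counted, because the window applies to post-baseline visits.

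**Step 1: what each late placebo injection removes.**

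| Group | Late placebo | PK visits excluded through Week 48 | On-schedule guselkumab values among them |
|---|---|---|---|
| Placebo | Week 4 | 4, 16, 32, 48 | 32, 48 |
| Placebo | Week 12 | 16, 32, 48 | 32, 48 |
| Guselkumab | Week 16 | 16, 32, 48 | 32, 48 |

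In the placebo group, the Week 4 and 16 samples precede the first guselkumab dose, so no exposure information is lost there. In the guselkumab group I do not count Week 16 as a wrongful loss: if the whole visit was late, that sample was itself mistimed. Week 56 is also excluded in all three cases but lies beyond the planned summaries.

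**Step 2: how many participants.** Let q be the chance that one injection is out of window. The documents do not give q, so it is assumed, with independence between visits. With k post-baseline placebo injections (2 in the placebo group, 1 in the guselkumab group), the share affected is 1 − (1 − q)^k. If losses are random, the standard error of a by-visit mean grows by 1/√(share kept), which is 1/(1 − q) in the placebo group and 1/√(1 − q) in the guselkumab group.

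| q (assumed) | Placebo group (n = 100) | SE factor | Guselkumab group (n = 200) | SE factor |
|---|---|---|---|---|
| 1% | 1 − 0.99² = 2.0% (2 people) | 1.01 | 1% (2 people) | 1.01 |
| 2% | 1 − 0.98² = 4.0% (4) | 1.02 | 2% (4) | 1.01 |
| 5% | 1 − 0.95² = 9.8% (about 10) | 1.05 | 5% (10) | 1.03 |
| 10% | 1 − 0.90² = 19.0% (19) | 1.11 | 10% (20) | 1.05 |

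Limiting the trigger to guselkumab brings these placebo-only losses to zero in both groups. The counts ignore overlap with other exclusions.

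**Step 3: the pre-dose sample.** Take a guselkumab-group participant who attends Week 4 on time, gives the pre-dose sample, and is dosed 8 to 14 days late. Protocol 6.4 accepts that delay, but the dose is outside ±7 days. The rule then removes the Week 4 sample, although a later event cannot have affected it.

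**Step 4: sample timing.** At Weeks 32 and 48 there is no administration to be out of window. SAP 5.7.1 and 5.1.1.1 contain no sentence about the date of the sample itself.

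**The case against.** The strongest reply is that the rule was meant for guselkumab only. It stands in a section on guselkumab concentrations, it applies to participants who received guselkumab, and most neighbouring criteria name the drug. That is plausible, and nothing shows that placebo was intended. The point is therefore an ambiguity whose literal reading does harm, not proof of a deliberate rule.

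Excluding data after a late guselkumab dose is a legitimate, conservative choice for summaries of the regimen as scheduled. A tolerance on time since last dose would be an alternative, but choosing it is a matter of preference. A PK analysis window narrower than the dosing allowance in Protocol 6.4 is also not a contradiction in itself.

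A reader might go further and infer three things that the documents do not support:

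- **Mistimed Week 32 and 48 samples are never excluded.** They are excluded after any earlier dosing deviation or out-of-window administration. SAP 5.7.1 also provides for further exclusions of incongruous PK data under a sponsor SOP, whose content is not given. All that can be said is that the SAP itself states no sample-timing rule.
- **Doses after Week 16 have no window at all.** The protocol gives ±7 days for all post-baseline visits. This is a mismatch between the two documents.
- **The data are lost to all PK work.** The exclusion is written for by-visit analyses. Population PK has its own plan and report, and the analyses by antibody status in SAP 5.7.2.1 do not invoke this rule.

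**Conclusion.** The point holds as a minor one. As written, the timing rule lets placebo injections remove valid guselkumab concentrations at Weeks 32 and 48, and it drops on-time pre-dose samples when the dose at that visit is late. For q between 1% and 10%, about 2% to 19% of the placebo group and 1% to 10% of the guselkumab group are affected. The standard error of a by-visit mean rises by at most about 11% and 5% respectively. These figures rest on the literal reading, the assumed q, independence between visits, and random loss. Because placebo timing has no stated link to exposure, the documents support a loss of precision but do not establish bias.

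The window mismatch and the missing sample-timing statement need reconciling in the text whatever q turns out to be. PK falls under the other objectives and these outputs are descriptive. No primary or major secondary test is affected.

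**What to change.** In SAP 5.1.1.1 and 5.7.1:

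1. State that only a *guselkumab* administration outside the window triggers the exclusion.
2. Keep a pre-dose sample that was itself drawn within the window, and exclude only later samples.
3. State the ±7-day PK analysis window for all post-baseline visits, so that it agrees with the protocol.
4. Either apply the ±7-day window to sample dates at Weeks 32 and 48, or state that the cited SOP does so.

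The cost is a few sentences and a small programming change. The protocol and SAP already require the dates and times of sampling, and any out-of-window administrations, to be recorded. The dosing allowance in Protocol 6.4 need not change for this purpose.
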